9.2.5 Subpopulations of interest

Elderly patients (≥65 years of age at index) will be considered a subpopulation of special interest, for which separate analyses will be performed.

Furthermore, the following patient groups will be considered as subpopulations of special interest, as they are contraindications for NOCDURNA use. Numbers permitting, sub-analyses will be performed according to the NOCDURNA and the LUTS group overall and by the elderly.

For the primary outcome:

- History of hyponatraemia
- Polydipsia
- Concomitant use of loop diuretics
- Concomitant use of glucocorticoids
- Congestive heart failure (chronic)
- Kidney disease (chronic kidney disease stage 3 and over)
- Syndrome of inappropriate antidiuretic hormone secretion (SIADH)

- Additionally, for the cardiovascular disease outcome: uncontrolled hypertension
- Additionally, for the thromboembolic event outcome: coagulation disorders

See Annex 3, Table A2 for diagnostic codes.

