9.3.3 Covariates

To describe the study population, information on following variables will be collected to the extent available in each data source for a period of at least 12 months before the index date:

- Demographics: age, gender, place of residence (country), migration or transfer out of the database

- Treatment indication (diagnosis preceding NOCDURNA prescription in the exposed group; diagnosis preceding LUTS-defining prescription in the LUTS patient group)

- Sodium concentration (Sweden/Denmark)
- Comorbidities
- Co-medications

These factors may be considered in the analysis as potential confounding factors or effect modifiers. The comorbidities and co-medications are to be measured by disease and drug codes are specified and defined by classification system codes in Annex 3 Definitions (Table A4). Refer to section 9.4 for description of data sources that will be used to collect information on covariates.

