Annex 3 Definitions of the LUTS cohort, outcome events and covariates

Table A1. ATC codes used to define the LUTS cohort

Characteristic	ATC code	Description
Overactive bladder	G04BD	Drugs for urinary frequency and incontinence
Benign prostatic hyperplasia	G04C	Drugs used in benign prostatic hypertrophy

Characteristic	ICD-10	ATC	Description
	code	code	
Hyponatraemia	E87.1		
Polydipsia	R63.1		
Loop diuretics		C03C	
Glucocorticosteroids		H02AB	
Congestive heart failure	150.2		Systolic (congestive) heart failure
	150.3		Diastolic (congestive) heart failure
	150.4		Combined systolic (congestive) and diastolic (congestive) heart failure
Chronic kidney disease	N18.3		Chronic kidney disease, stage 3 (moderate)
	N18.4		Chronic kidney disease, stage 4 (severe)
	N18.5		Chronic kidney disease, stage 5
	N18.6		End stage renal disease
Syndrome of inappropriate antidiuretic hormone secretion	E22.2		
Uncontrolled hypertension	I16		Hypertensive crisis
	167.9		Hypertensive encelopathy
Coagulation disorders	D68.0		Von Willebrand's disease
	D68.5		Primary thrombophilia
	D68.6		Other thrombophilia

Table A2. Codes used to define subpopulations of interest

Outcome	ICD-10 code	Description
Hyponatremia		
Hyponatraemia	E87.1	
Hyponatremia (biochemical definition)	n/a	Will be ascertained using biochemical definition: serum sodium concentration <135 mmol/L (mild hyponatraemia) Evaluated only in Denmark
Major cardiovascular events (MACE)	
Myocardial infarction	121, 122	
Stroke, ischemic	163.3-163.9, 166	
Major venous thromboembolic	c events	
Pulmonary embolism	126	
Deep vein thrombosis	180.1–180.9	
Portal vein thrombosis	181	
Mortality		
All-cause mortality	Any	Death from any cause
Heart failure		
Heart failure	150	

Table A3. Codes used to define outcome events

Table A4. Codes used to define covariates

Covariate	ICD-10 code	ATC code	Description/comment
Comorbidities			
History of hyponatraemia, MACE	Please refer to		
and VTE	Table A1		
Polyuria	R35		Polyuria
Diabetes mellitus	E10		Type 1 diabetes mellitus
	E11		Type 2 diabetes mellitus
	E12		Malnutrition-related diabetes
			mellitus
	E13		Other specified diabetes mellitus
	E14		Unspecified diabetes mellitus
Diabetes insipidus	E23.2		
Overactive bladder	N31.0		Uninhibited neuropathic bladder, not elsewhere classified
	N31.2		Flaccid neuropathic bladder, not elsewhere classified
	N31.9		Neuromuscular dysfunction of bladder, unspecified
	N39.4		Other specified urinary incontinence

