	R39.1		Other difficulties with micturition
		G04BD	Drugs for urinary frequency and incontinence
Benign prostatic hyperplasia	N40		Benign prostatic hyperplasia
	D29.1		Benign neoplasm of prostate
		G04C	Drugs used in benign prostatic hypertrophy
Urinary tract infection	N39.0		Urinary tract infection, site not specified
	N30		Cystitis
	N10		Acute tubulo-interstitial nephritis
Polydipsia	R36.1		Excessive thirst
Heart failure	150		
Hypertension	110		Essential (primary) hypertension; medications to be used as proxy (see below under co- medications)
Hyperlipidaemia	E78		Disorders of lipoprotein metabolism and other lipidaemias; medications to be used as proxy (see below under co-medications)
Atrial fibrillation	148		
Obesity	E66		
Kidney disease	N18		
	N19		
Cystic fibrosis	E84		
Pre-eclampsia	011		Pre-eclampsia superimposed on chronic hypertension
	O14		Pre-eclampsia

Covariate	ICD-10 code	ATC code	Description/comment
Chronic lung disease	J40-J47		Chronic lower respiratory
······································			diseases
	J60-J70		Lung diseases due to external
			agents
	J80		Adult respiratory distress
			syndrome
	J82		Pulmonary eosinophilia, not
			elsewhere classified
	J84		Other interstitial pulmonary
	105 100		diseases Other diseases of the respiratory
	J95-J99		system
Liver disease	K70-K77		Diseases of liver
			Diseases of liver
	F10		F10 (mental and behavioural
		N07BB	disorders due to use of alcohol)
			and N07BB (drugs used in
			alcohol dependence) included as
	000.040		proxy measures of liver disease
Cancer	C00-C43		Cancer excluding non-melanoma
	C45-C97		skin cancer C61 (prostate cancer) and C67
			(bladder cancer) of special
			interest
Dementia	F00		Dementia in Alzheimer disease
	F01		Vascular dementia
	F02		Dementia in other diseases
			classified elsewhere
	F03		Unspecified dementia
	F04		Organic amnesic syndrome, not
			induced by alcohol and other
			psychoactive substances
	G30		Alzheimer's disease
	G31.0		Frontotemporal dementia
	G31.1		Senile degeneration of the brain
Number of hospitalisations	Any		Marker of overall health; to be
			assessed in the year before the index date
Number of emergency room	Δηγ		Marker of overall health; to be
visits	Any		assessed in the year before the
			index date
Co-medications, including drugs	that may increase th	ne risk of hypona	
Loperamide		A07DA03	
Antidiabetics		A10	A10BB (sulfonylureas including
			chlorpropamide), of special
			interest
Amiodarone		C01BD01	
Antihypertensives		C02	

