1.2.2 Presentation of Inferential Results

Frequentist inferential results will be presented using the respective point estimates, their Standard Errors and two-sided 95% confidence intervals unless otherwise stated.

Table shells per type of analysis and standard figures are also provided in section 14 and for the meta-analysis and the interpretation it is important that the table shells are followed. The figures in the 2021 report are not expected to be completely harmonized because the data from the different countries will be variable making a fix determination of the axis scale is difficult prior to reviewing the data.

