The analysis will first calculate the treatment cessation date and then within a 14 days window before the treatment cessation date examine if there is a MACE or VTE event reported from the intensive care register.

Secondary objective 9: Incidence rate in patients stratified according to the label by proxy

The analysis of this outcome will be performed analogous to that of incident events of symptomatic hyponatraemia but only for the Nocdurna ® patients. The subgroup of patients adhering to the label will be defined by a proxy based on diagnosis and contra-indications as stated in the SmPC and the data for classifying the patients according to contraindications should be done as available in the respective registries.

Two population will be created for all Nocdurna ® patients, one with contra-indication for treatment and another as the remaining Nocdurna ® patients without contra-indication. The contra-indication for treatment must be present before the first recorded dispensation of Nocdurna ®.

The following diseases will be considered as contraindications for the prescription of Nocdurna ®, if the diseases are found before or at the index date.

- History of hyponatraemia
- Polydipsia
- Congestive heart failure (chronic)
- Kidney disease (chronic kidney disease stage 3 and over)
- Syndrome of inappropriate antidiuretic hormone secretion (SIADH)

The ICD 10 codes for the above can be found in the given in Table 71. The analysis will be done by using the SAS macro 'Nocdurna_mac' and changing the macro call with 'compare=Off label' and creating a class group with 'Off label' instead of 'LUTS' as described in section 16.1

The analysis of the sub-population will be done for the primary objective and for secondary objective 2, 3, 4, 5a, 5b and 6.

Observe that this analysis is changed from the description in the study protocol.

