SOURCE DOCUMENT: TABLE1.SAS GENERATED: 22:53:48 16JAN2021 DB version DEV: Simulated data, USERID: [name]

Figure 6. Primary objective. A Cox regression showing time to first event symptomatic hyponatraemia event stratified by patient group and age class in *country*. Survival function for different age grous Nocdurna

Footnote: The figure should have 8 lines, one for each age group (3) and treatment (2). SOURCE DOCUMENT: COX1.SAS GENERATED: 22:53:48 16JAN2021 DB version DEV: Simulated data, USERID: [name]

Table 10	Secondary ob	iective 1 Der	nooranhic and	health char	racteristics in	country
1 abic 10.	Secondary 00		nographic and	incartin cha	lacteristics in	1 country.

	All Nocdurna ® patients	Nocdurna ®, Male	Nocdurna ®, Female	All LUTS patients	LUTS, Male	LUTS, Female
Age (year)						
Ν	230	100	230	100	230	100
Mean (SD)	61.17 (8.36)	62.81 (9.00)	61.17 (8.36)	62.81 (9.00)	61.17 (8.36)	62.81 (9.00)
Median	62.05	63.13	62.05	63.13	62.05	63.13
Range	44.7 , 82.3	40.0 , 85.0	44.7 , 82.3	40.0 , 85.0	44.7 , 82.3	40.0,85.0
IQR	56.0 , 74.0	55.0,75.0	56.0 , 74.0	55.0,75.0	56.0 , 74.0	55.0,75.0
Missing values	0	0	0	0	0	0
Repeat above 7 limes for						
Number of hospitalisations						
Number of emergency room visits						
Exposure time						

Ferring Pharmaceuticals

ender, n and (%)						
Male	99 (43)	99 (43)	N/A	49 (49)	49 (49)	N/A
Female	131 (57)	N/A	131 (57)	51 (51)	N/A	51 (51)
epeat the above 3 lines or						
olyuria R35, please heck national nplementation of R35	Xx (xx)	Xx (xx)	Xx (xx)	Xx (xx)	Xx (xx)	Xx (xx)
olyuria R35.9A	Xx (xx)	Xx (xx)	Xx (xx)	Xx (xx)	Xx (xx)	Xx (xx)
lykturi R35.9B	Xx (xx)	Xx (xx)	Xx (xx)	Xx (xx)	Xx (xx)	Xx (xx)
ollakisuri R35.9C	Xx (xx)	Xx (xx)	Xx (xx)	Xx (xx)	Xx (xx)	Xx (xx)
biabetes mellitus; E10, 11, E12, E13 and E14	Xx (xx)	Xx (xx)	Xx (xx)	Xx (xx)	Xx (xx)	Xx (xx)
viabetes insipidus, E23.2	Xx (xx)	Xx (xx)	Xx (xx)	Xx (xx)	Xx (xx)	Xx (xx)
overactive bladder, N31.0, 131.2, N31.9, N39.4, 39.1 and ATC G04BD	Xx (xx)	Xx (xx)	Xx (xx)	Xx (xx)	Xx (xx)	Xx (xx)
enign prostatic yperplasia, N40, D29.1 nd ATC G04C	Xx (xx)	Xx (xx)	Xx (xx)	Xx (xx)	Xx (xx)	Xx (xx)
rinary tract infection, 39.0, N30, N10	Xx (xx)	Xx (xx)	Xx (xx)	Xx (xx)	Xx (xx)	Xx (xx)
olydipsia, R36.1	Xx (xx)	Xx (xx)	Xx (xx)	Xx (xx)	Xx (xx)	Xx (xx)
leart failure, 150	Xx (xx)	Xx (xx)	Xx (xx)	Xx (xx)	Xx (xx)	Xx (xx)
lypertension, I10	Xx (xx)	Xx (xx)	Xx (xx)	Xx (xx)	Xx (xx)	Xx (xx)
lyperlipidaemi, E78	Xx (xx)	Xx (xx)	Xx (xx)	Xx (xx)	Xx (xx)	Xx (xx)

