Table 58. Sensitivity analysis. Incidence of acute exacerbation of congestive heart failure in *country* with prescribed intake used instead of 1 tablet per day in Denmark and Sweden, if possible. LUTS patients are unchanged.

Meta-analysis

Table 59. Meta-analysis. Combined demographic and health characteristics in the study.

	Nocdurna ®				LUTS			
	Denmark	Germany	Sweden	Overall	Denmark	Germany	Sweden	Overall
Age (year)								
N	Xx	Х	Xx	Xx	Xx	Xx	Xx	Xx
Mean (SD)	Xx (xx)	Xx (xx)	Xx (xx)	Xx (xx)	Xx (xx)	Xx (xx)	Xx (xx)	Xx (xx)
Range	Xx, xx	Xx, xx	Xx, xx	Xx, xx	Xx, xx	Xx, xx	Xx, xx	Xx, xx
Missing values	х	х	х	Х	х	х	x	х
Repeat above 7 lines for								
Number of hospitalisations								
Number of emergency room visits								
Gender, n and (%)								
Male	Xx (xx)	Xx (xx)	Xx (xx)	Xx (xx)	Xx (xx)	Xx (xx)	Xx (xx)	Xx (xx)
Female	Xx (xx)	Xx (xx)	Xx (xx)	Xx (xx)	Xx (xx)	Xx (xx)	Xx (xx)	Xx (xx)
Repeat the above 3 lines for								
Polyuria R35								
Diabetes mellitus; E10, E11, E12, E13 and E14								
Diabetes insipidus, E23.2								
Overactive bladder, N31.0, N31.2, N31.9, N39.4, R39.1 and ATC G04BD								
Benign prostatic hyperplasia, N40, D29.1 and ATC G04C								
Urinary tract infection, N39.0, N30, N10								
Polydipsia, R36.1								

Heart failure, I50

Hypertension, I10

Hyperlipidaemi, E78

Atrial fibrillation, I48

Obesity, E66

Kidney disease, N18, N19

Cystic fibrosis, E84

Pre-eclampsia, O11, O14

Chronic lung disease, J40-J47, J60-J70, J80, J82, J84, J95-J99

Liver disease, K70-K77, F10 and ATC N07BB

Cancer, C00-C43, C45-C97

Prostate cancer, C61

Bladder cancer, C67

Dementia F00, F01, F02, F03, F04, G30, G31.0, G31.1

Co-medication

Loperamide, A07DA03

Antidiabetics, A10

Sulfonylureas including chlorpropamide, A10BB

Amiodarone, C01BD01

Antihypertensives, C02

Diuretics, C03

Special diuretics, C03A, C03B, C03C, C03D and C03E Beta blocking agents, C07

Special beta blocking agents, C07B, C07C and C07D

Calcium channel blockers and diuretics, C08G

ACE inhibitors, C09A

Special ACE inhibitors, C09BA

Angiotensin II receptor blockers, C09C

Angiotensin II receptor blockers (combinations), C09D

Lipid-modifying agents, C10

Vasopressin and analogues (incl. desmopressin), H01BA

Systemic corticosteroids, H02

Antiepileptics, N03A

Carbamazepine and lamotrigine, N03AF01 and N03AX09

Non-selective monoamine reuptake inhibitors, N06AA

Selective serotonin reuptake inhibitors, N06AB

Chlorpromazine, N05AA01

NSAIDs, M01A

Opioids, N02A

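### Polydipsia is coded R63.1 where contraindicated patients are identified but R36.1 where its baseline prevalence is reported; the lists must be reconciled.

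*Protocol*

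**What the plan says.** Two sets of code lists are in force, and they disagree on polydipsia.

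- **Subpopulations and contraindications.** Protocol section 9.2.5 lists polydipsia among the subpopulations for the primary outcome and points to the annex: "See Annex 3, Table A2 for diagnostic codes". Table A2 there has "Polydipsia R63.1". The SAP's text on secondary objective 9 names polydipsia as one of five contraindicating conditions and says "The ICD 10 codes for the above can be found in the given in Table 71". Table 71 contains R63.1.
- **Covariates and baseline tables.** Protocol section 9.3.3 says that comorbidities and co-medications are "specified and defined by classification system codes in Annex 3 Definitions (Table A4"). Table A4 has "Polydipsia R36.1 Excessive thirst". SAP Table 73 repeats that row and is marked as copied from the protocol. The shell of SAP Table 10 has "olydipsia, R36.1" (first letter lost in the text available) and the shell of Table 59 has "Polydipsia, R36.1".

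SAP section 2 ties the risk-factor prevalences of secondary objective 1 to Table 10. SAP section 1.2.2 tells the programming groups that "for the meta-analysis and the interpretation it is important that the table shells are followed".

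**The concern.** The two codes differ by a transposition of digits, yet both lists are working instructions. One classifies Nocdurna patients as treated within or outside the label. The other produces the baseline description.

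Polydipsia belongs to both: it is a contraindication, and its prevalence is part of a stated objective. If the lists are followed literally, the report will give a polydipsia prevalence that does not match the polydipsia used to classify patients. If one country's programmers notice the discrepancy and correct it locally while the others do not, Table 59 will combine different codes under one label across Denmark, Germany and Sweden.

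**Working it through.** No arithmetic figure is at issue. The check sets every coded appearance of polydipsia side by side and follows each one to the output it feeds.

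| Place | Code | Feeds |
|---|---|---|
| Protocol Annex 3, Table A2 | R63.1 | Subpopulations (protocol 9.2.5) |
| SAP Table 71 | R63.1 | Contraindication split (secondary objective 9) |
| Protocol Annex 3, Table A4 | R36.1 | Covariates (protocol 9.3.3) |
| SAP Table 73 | R36.1 | Covariates |
| SAP Table 10 shell | R36.1 | Country baseline table |
| SAP Table 59 shell | R36.1 | Combined baseline table |

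**Count.** R63.1 stands in 2 places and R36.1 in 4. Table 11 (by contraindication), Table 12 (by sodium measurement) and Table 28 (heart-failure population) are to repeat the Table 10 structure. The affected baseline tables are therefore 2 printed shells + 3 inherited = 5.

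**Is it a text-extraction error?** No. Each version recurs independently in the protocol and in the SAP, and both covariate lists pair R36.1 with the same description. In the text available, the row labels of Table 71 are missing, so its link between R63.1 and polydipsia rests on order. The codes run E87.1, R63.1, I50, N18.3 to N18.6, E22.2. That matches the SAP's list for objective 9: hyponatraemia, polydipsia, heart failure, kidney disease, SIADH. Protocol Table A2 states the link directly.

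**Is it an announced change?** SAP section 13 describes the revision of the contraindication definition but says nothing about the polydipsia code.

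**Consequence in Table 11.** This table splits Nocdurna patients by contraindication status and repeats the Table 10 rows. SAP section 6.1.1 takes baseline diagnoses recorded before or at the index date. The objective 9 text uses the same window when it lists the contraindicating diseases.

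- With a single code, every patient counted in the polydipsia row would be in the contraindicated group, and the polydipsia cell for patients without contraindications would be zero by construction.
- With two codes, a patient with only R63.1 is in the contraindicated group but not in the polydipsia row.
- With two codes, a patient with only R36.1, and no other contraindication, is in the polydipsia row of the group without contraindications.

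The table would then be inconsistent with its own grouping.

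**Do the models use the covariate code?** SAP section 10.1.2 gives the independent variables as treatment, age class and gender. Section 10.2.8 names age class and gender as the confounders. The model statement printed in section 16.1 contains only those terms. The contraindication split takes its codes from Table 71. None of these uses R36.1.

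**The case against.** The strongest reply is that this is a probable slip in one descriptive row among dozens. It touches neither the primary outcome nor any specified rate or ratio. SAP section 16.3 adds that no common program for the baseline description has been developed, and that each institution is expected to use its own software. The code therefore sits in a list and a shell, not in distributed code, and an alert programmer might catch it. All of that stands as a limit on the size of the problem. It does not remove the problem, because the SAP asks for the shells to be followed and the row belongs to a stated objective.

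A reader might infer more than the documents support:

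- **That adjusted models are wrong.** Protocol section 9.3.3 says only that covariates may be considered as confounders or effect modifiers, and no specified model includes polydipsia.
- **That R36.1 counts an unrelated condition.** The documents never say so; they label it as excessive thirst and give R63.1 no description. What they show is that a different code is used.
- **That the error covers both cohorts in three countries in all five tables.** Table 11 is restricted to Nocdurna patients and Table 12 to Denmark.
- **That the documents prove R63.1 correct.** They do not settle it. They lean that way: the digits are transposed, and the SAP kept R63.1 when it revised the contraindication list, whereas Table 73 was simply carried over from the protocol.

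**Conclusion.** The contradiction is real and affects output. As written, the polydipsia prevalence for secondary objective 1 comes from a different code than the one used to identify contraindicated patients, and Table 11 need not agree with its own grouping.

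The size is one descriptive row in five baseline tables, repeated in the block for patients aged 65 or over where the shell asks for it. How many patients are affected cannot be stated, because the documents give no prevalence for either code. The specified incidence rates, incidence rate ratios and contraindication split do not use the covariate-list code.

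This rests on two assumptions: that the lists and shells are followed as printed, and that R63.1 in Table 71 stands for polydipsia. The limitation to descriptive output also presumes that R63.1 is the intended code. If the ICD-10 check showed otherwise, the contraindication split itself would need correcting, so the check should be made and not taken for granted. The point merits correction before the final tables, not a change to the analysis.

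**What to change.** Reconcile the lists to one polydipsia code, checked against the ICD-10 versions used in Denmark, Germany and Sweden. If R63.1 is confirmed, as the documents suggest, replace R36.1 in protocol Table A4, SAP Table 73 and the shells of Tables 10 and 59. Tables 11, 12 and 28 then follow automatically. Tell all three programming groups at the same time, so that the correction is not made in some countries only. Each group should also confirm that its data extract contains the chosen code.

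A simple test afterwards is that the polydipsia row in Table 11 should be empty for patients without contraindications.

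The cost is one code corrected in two lists and two shells. If an extract turns out not to contain the code, a supplementary data request may be needed; the documents do not show whether that is the case.
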